Title: Can rTMS Enhance Somatosensory Recovery After Stroke?

NCT 02811913

Date : 10/8/2020

Last version of IRB-approved Research plan - 2/12/2019

Abbreviated protocol

Specific Aims. There is a confluence of evidence that supports the proposed work. First, sensory recovery is a product of brain plasticity and can be achieved even in chronic stages after stroke as demonstrated by preliminary data and evidence from the literature. Second, rehabilitation therapies can be enhanced with rTMS. Both post-stroke rehabilitation and rTMS are well established methodologies in the investigators' laboratories. Third, there is limited knowledge regarding the most effective type of rTMS (facilitatory or inhibitory) that would enhance recovery of somatosensation for individuals in chronic stages after stroke. Therefore, the main objective of this study is to test the feasibility and preliminary efficacy of a novel approach to treat sensory deficits after stroke with a combination of repetitive Transcranial Magnetic Stimulation (rTMS) and peripheral arm and hand sensory therapy. We propose to address the two study Aims by testing the following hypotheses. Aim 1: Test effect of rTMS of the contralesional S1 region on sensory function Hypothesis 1a. Facilitatory rTMS of contralesional S1 produces a greater response versus sham rTMS, according to a measure of tactile discrimination. Hypothesis 1b. Facilitatory rTMS of contralesional S1 produces a greater response versus inhibitory rTMS in improving tactile discrimination. Aim 2: Characterize neurophysiological changes in response to rTMS of contralesional S1. Hypothesis 2: Repetitive TMS of the contralesional S1 region leads to functional brain changes.

Study design overview. We will enroll subjects who are at least 6 months from onset of the first ever stroke and who have residual sensory deficits. There will be 3 treatment sessions at least 7 days apart consisted of rTMS and sensory re-education therapies. Prior to the first intervention session, there will be a baseline data collection session. rTMS will target the contralesional (intact hemisphere) primary sensory region. rTMS stimulation will be either facilitatory, i.e. temporary increasing brain activity, or inhibitory, i.e. temporary decreasing brain activity. rTMS will be administered in combination with peripheral sensory therapies. The order of the sessions will be randomly assigned. All evaluations will be performed by a therapist who will be blinded to the site or the type of rTMS.

rTMS intervention. We will use a frameless stereotaxy system, Brainsight 2(Rogue Research, Inc., Montreal, QC) to perform image-guided TMS. The optimal stimulation site will be approximately 2 cm posterior to the hand motor area and to a hotspot for eliciting MEPs in first dorsal interossues (FDI) (Schneider 2010).

A Magstim Super Rapid 200² magnetic stimulator (MagStim Company Ltd., Wales, UK) will be used along with a flat 70 mm figure-of-eight magnetic air-cooled coil with a maximum magnetic field strength of 1.5 T (Tesla) and an average inductance of 15.5 μ H. The figure-of-eight coil produces a focal stimulation point in the middle of the junction between the two circular coil elements. We will use both inhibitory and facilitatory rTMS stimulation protocols (Pleger 2006,Huang 2005). These protocols have been effectively used in achieving changes in somatosensation in healthy adults (Premji 2010,Ragert 2008). Facilitatory rTMS protocol will consist of 5Hz rTMS at 90% resting MT; a total of 1250 pulses (Pleger 2006), (Rossini 1999,Rossini 1994). Inhibitory rTMS protocol will consist of 1Hz rTMS for a total of 1200 pulses. Sham intervention will be provided using a sham coil. The active coil is a flat 70 mm figure-of-eight magnetic air-cooled coil with a maximum magnetic field strength of 1.5 T (Tesla) and an average inductance of 15.5 μ H; the sham coil is identical in appearance to the active coil but has a maximum magnetic field of 0.2T and an average inductance of 2.8 μ H which is well below stimulus threshold while producing similar sensory and auditory effects.

Peripheral Sensory stimulation will consist of vibratory stimulation (5 minutes), and functional neuromusclular electrical stimulation (5 minutes) of the affected arm and will be administered simultaneously after the rTMS treatments.

Aim1 (testing Hypothesis 1a and 1b) Test effect of rTMS of the contralesional S1 region on sensory function The primary outcome measures will be two point discrimination. It will be collected at 3 time points during the treatment session (once before and 2 times after the rTMS: immediately after and 1 hour after. **Two-point discrimination** will be measured with Disk-Criminator disks (Baltimore, MD) by determining subjects' ability to distinguish if the touch consisted of one or two points.

Aim 2 to test Hypothesis 2: Characterize neurophysiological changes in response to rTMS of contralesional S1.. The primary outcome measure to test Hypothesis 2 we will be SEP . It will be collected at 3 time points during the treatment session (once before and 2 times after the rTMS: immediately after and 1 hour after. Somatosensory evoked potentials (SEP). SEP will be induced by stimulation of the median nerves at the wrist with a square pulse of 0.2ms delivered at 3Hz at an intensity of 2.5 times above sensory threshold but below pain threshold (Delberghe 1990). SEPs will be recorded with Ag-AgCl scalp electrodes placed on the scalp over S1 cortical region keeping impedance at $5k\Omega$ (2 cm posterior to the C3 and C4 coordinate, International 10-20 system (Nuwer 1994)), referenced to a frontocentral Fz electrode and grounded with a clavicular electrode. Location of the scalp electrodes will be digitized with Brainsight system (Rogue, Montreal) for later coregistration with the TMS data. SEP will be acquired with a Neuroscan system (Compumedics, Charlotte, NC) at a sampling rate of 1kHz using a 10 DC gain and band filtered (low pass 40 Hz, high pass 0.1 Hz, notch at 60 Hz). SEP data will be collected in blocks of 500 epochs. The N20/P30 components will be identified based on their latency and polarity and their peak-to peak amplitude measured. N20 is a negative peak within a primary sensory receptive region at 20 ms following peripheral nerve stimulus (Allison 1989, Lueders 1983). We expect to find changes in the amplitude and possibly latency of N20/P25 SEP component (Premji 2010).

Inclusion criteria

- Medically stable and at least 6 months after first ever stroke
- Cognition sufficiently intact to give valid informed consent to participate (Etchells 1999)
- Ability to follow two stage commands
- Impaired but not absent ability to feel touch, vibration, movement of affect arm
- Sufficient endurance to participate in the study
- Age > 18

Exclusion Criteria

- •
- More than one ischemic strokes or stroke affecting both sides
- Significant neglect for those with left-sided deficits
- Acute or progressive cardiac, renal, respiratory, neurological disorders or malignancy.
- Any psychiatric diagnosis or active psychological condition
- Presence of implanted medical devices such as cardiac pacemakers and defibrillators, intrathecal drug delivery pumps, or spinal cord, vagus nerve or similar stimulators, or cochlear implants
- Presence of metallic hardware that would be in close contact with the TMS discharging coil such as intracranial implants, aneurysm clips, plates, electrodes

- Past history of seizures or unexplained loss of consciousness
- Family history of medication refractory epilepsy
- History of substance abuse within the last 6 months
- Chronic sleep deprivation, ongoing untreated sleep disorder
- Concurrent ototoxic medication (aminoglycodides, cisplantine)
- Pregnancy or pregnancy planning during the study period
- Currently taking medications or substances that lower the threshold for onset of seizure: imipramine, amitriptyline, doxepine, nortriptyline, maprotiline, chlorpromazine, clozapine, foscarnet, ganciclovir, ritonavir, amphetamines, cocaine (MDMA, ecstasy), phencyclidine (PCP, angel's dust), ketamine, gamma-hydroxybutyrate, alcohol, theophylline.
- Individuals will be excluded if they recently stopped taking the following drugs within the past 6 months: alcohol, barbiturates, benzodiazepines, meprobamate and chloral hydrate.
- Inability to understand English
- Unavailable to participate in the study

Statistical Analysis Plan. The outcome measures for the aims are typical longitudinal data. Linear mixed models (LMM) will be fitted for the data. LMM is a generalization of the standard linear model, permitting the data to exhibit correlation and nonconstant variability.

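### Does Aim 1 need a planned comparison of inhibitory rTMS with sham, beyond Hypotheses 1a and 1b?

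*Combined protocol and SAP*

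**What the plan says.** The Specific Aims state the motivation as "there is limited knowledge regarding the most effective type of rTMS (facilitatory or inhibitory) that would enhance recovery of somatosensation". Aim 1 is worded broadly: "Test effect of rTMS of the contralesional S1 region on sensory function". Two directional hypotheses follow:

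- The first, numbered 1a, takes sham as the comparator: "Facilitatory rTMS of contralesional S1 produces a greater response versus sham rTMS, according to a measure of tactile discrimination".
- The second, numbered 1b, sets the two active types against each other: "Facilitatory rTMS of contralesional S1 produces a greater response versus inhibitory rTMS in improving tactile discrimination".

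Hypothesis 2, on evoked potentials, reads "Repetitive TMS of the contralesional S1 region leads to functional brain changes" and names neither a type of rTMS nor a comparator.

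The Study design overview says "There will be 3 treatment sessions at least 7 days apart" and that session order is randomised. The rTMS intervention section adds "We will use both inhibitory and facilitatory rTMS stimulation protocols" and "Sham intervention will be provided using a sham coil". The methods paragraph for Aim 1 refers back to 1a and 1b only, and gives one measurement before rTMS and two after. The Statistical Analysis Plan names linear mixed models and lists no contrasts, not even 1a and 1b.

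**The concern.** There are three conditions and so three pairwise differences, but only two are planned. The missing one sets an active type against sham, and the rationale treats that type as a live candidate. If 1a and 1b both succeed, facilitatory rTMS ranks first, but inhibitory rTMS could still be better than sham, the same as sham or worse. If 1b came out reversed while 1a was not significant, inhibitory rTMS would look the better of the two without any planned comparison with control. A contrast chosen after the results are seen is open to selective reporting. On that view the trial would give every subject an inhibitory session and plan no statement of what it does.

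**Working it through.** **1. What is planned.** Write F, I and S for the mean responses after facilitatory, inhibitory and sham sessions. 1a is F − S and 1b is F − I. Neither Hypothesis 2 nor the Statistical Analysis Plan supplies I − S. The factual premise is correct.

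**2. What the planned pair determines.** I − S = (F − S) − (F − I). Two positive terms do not fix the sign of their difference, so the logical premise is correct too. The same identity shows that the quantity is not lost. If one mixed model is fitted with session type as a three-level factor, the I − S estimate is the difference of the two planned estimates, and the model supplies its standard error.

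**3. Assumptions for the illustration.** The documents give no sample size, variance, effect size, significance level or sidedness. Assumed: each subject has one session of each type, variances are equal, and tests are two-sided at 5%. Each condition mean is given standard error 1/√2. Each contrast then has variance 1/2 + 1/2 = 1. Contrasts 1a and 1b share F, so their correlation is (1/2)/1 = 0.5. The variance of I − S is 1 + 1 − 2 × 0.5 = 1, so it is as precise as the planned contrasts. The effect d is the one detected with 80% power: 1.960 + 0.842 = 2.802. Brackets below give the range from 50% power (d = 1.960) to 90% power (d = 3.242). S is set to 0; results are from 4,000,000 normal draws, with both-succeed under pure harm from a separate run.

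| True F, I | Result on 1a and 1b | Probability |
|---|---|---|
| 2d, d (inhibitory helps) | both succeed | 80% (50–90%) |
| d, −d (inhibitory harms) | both succeed | 80% (50–90%) |
| d, 0 (only facilitatory acts) | both succeed | 69% (33–83%) |
| 0, −d (pure inhibitory harm) | both succeed | 2.5% (2.2–2.5%) |
| 0, −d | 1b succeeds, 1a does not | 77.5% (48–88%) |
| 0, d (only inhibitory helps) | 1b reversed, 1a not significant | 77% (48–86%) |

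The first two rows show the ambiguity: the same planned result under opposite inhibitory effects.

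**4. Can the pair tell facilitatory benefit from inhibitory harm?** Compare rows 3 and 4: joint success in 69% against 2.5%. Under pure harm the usual pattern is 1b alone (77.5%); under pure facilitatory benefit that pattern occurs in about 80% − 69% = 11%. So 1b read alone cannot separate the two explanations, but 1b read with 1a does so in most trials at 80% power, and less well at 50%.

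**5. What an added I − S interval would show.** Given joint success, its 95% interval excludes zero in the true direction in 76% (33–89%) of trials in each of the first two scenarios. With I = S, the case nearest the plan's own hypotheses, it excludes zero by chance in 2.6% (1.4–3.3%). If only inhibitory rTMS helps and 1b reverses with 1a not significant, the interval shows benefit in 87% (69–93%) of those trials. This last case is where it tells most.

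**6. Cost if it became a third formal test.** At 5% each, unadjusted family-wise error would rise from 1 − 0.95² = 9.8% to 1 − 0.95³ = 14.3% if the tests were independent, or from about 9.1% to 12.2% with the shared-condition correlation. Going from two to three Bonferroni-adjusted tests (0.025 to 0.0167 each) needs about 10% more subjects for 80% power per contrast. A descriptive estimate avoids that cost but supports no formal claim.

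**The case for a change.** The strongest case for a change is that it is almost free. One sentence could name I − S with its 95% interval as a secondary estimate, with no new visit and no effect on the error rates of 1a and 1b. Naming it beforehand guards against reporting it only when it looks interesting, and Aim 1 as worded covers the effect of either type. If 1b fails or reverses, a reader will want this estimate first.

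Most of that stands as a preference. It does not show that anything planned is wrong. The rationale asks which of two types is more effective, and 1b answers that directly. Whether inhibitory rTMS differs from sham is a further question. Nothing in the Statistical Analysis Plan excludes the estimate, and an analyst facing a reversed 1b would take it from the fitted model as a matter of course. The gap is also not specific to this contrast: the plan lists none, and it does not say how the one pre-treatment and two post-treatment measurements form a response, which any I − S sentence would first need. Since the document is headed as abbreviated, the fuller plan may list more.

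**Conclusion.** The observation is accurate, but no change follows. Carried out as written, the plan supports sound conclusions on 1a and 1b, and joint success answers which type works best. The open point is whether inhibitory rTMS itself differs from sham. It matters mainly if 1b fails or reverses, and the estimate is then available from the same model by subtraction. Confining the planned hypotheses to two contrasts is a fair trade-off in a study of feasibility and early efficacy, where a third formal test would cost error control or about 10% more subjects. The planned pair separates pure facilitatory benefit from pure inhibitory harm well at 80% power (joint success 69% against 2.5%) and less well at 50% (33% against 2.2%).

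This rests on each subject having one facilitatory, one inhibitory and one sham session, which is inferred from the three sessions and three conditions, and on one model being fitted to all three. The effect sizes, equal variances and two-sided 5% level are assumptions. The identity and the conclusion do not depend on them.

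### Nothing in the plan ensures that facilitatory, inhibitory and sham rTMS fall equally often in sessions 1, 2 and 3; balanced orders and a session term would be a cheap improvement

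*Combined protocol and SAP*

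**What the plan says.** The Study design overview sets out the sessions: "There will be 3 treatment sessions at least 7 days apart consisted of rTMS and sensory re-education therapies". It adds that "rTMS will be administered in combination with peripheral sensory therapies", with no exception for sham, and gives the allocation rule in one sentence: "The order of the sessions will be randomly assigned". The rTMS intervention section describes a facilitatory and an inhibitory protocol and adds "Sham intervention will be provided using a sham coil". Three conditions and three sessions imply one condition per session in each subject. That mapping is the natural reading, but it is not written out.

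Hypothesis 1a is "Facilitatory rTMS of contralesional S1 produces a greater response versus sham rTMS, according to a measure of tactile discrimination", and Hypothesis 1b compares facilitatory with inhibitory rTMS. Two-point discrimination is read three times in each session: "once before and 2 times after the rTMS: immediately after and 1 hour after".

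On the model, the Statistical Analysis Plan paragraph says "Linear mixed models (LMM) will be fitted for the data". It lists no fixed effects, so it names no session, sequence, carry-over or pre-session term. No sample size is given. The Specific Aims describe the objective as feasibility and preliminary efficacy.

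**The concern.** Both contrasts in Aim 1 compare conditions given in different sessions, so anything that changes from session 1 to session 3 can enter them. The plan's own rationale makes such a change plausible. It holds that "sensory recovery is a product of brain plasticity and can be achieved even in chronic stages after stroke", every session adds vibration and electrical stimulation of the affected arm, and the two-point task is done nine times (3 readings in each of 3 sessions). Response within a session could grow with practice and therapy, or shrink as room to improve is used up, whatever the rTMS type.

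Random order cancels such a drift over repeated trials, but not in the single trial that is run. If facilitatory rTMS happens to fall later than sham, part of the drift sits in the Hypothesis 1a contrast. Equal use of all orders would remove this by design and a session term would remove most of it in the analysis. The plan commits to neither.

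**Working it through.** The plan states no sample size, drift, standard deviation or significance level, so there is no figure to reproduce. The check takes n = 12 to 60 as assumed values and assumes that each subject's order is drawn independently and uniformly from the six possible orders.

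**Imbalance per subject.** Let D be the session number of facilitatory minus that of sham. D is ±1 with total probability 4/6 and ±2 with total probability 2/6. Its mean is 0 and its variance is (4/6)·1 + (2/6)·4 = 2.

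**Imbalance per trial.** The mean of D over n subjects has SD √(2/n). The probability that it reaches half a session, computed exactly by convolving the distribution of D, is:

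| assumed n | SD (sessions) | P(difference ≥ 0.5 session) |
|---|---|---|
| 12 | 0.41 | 26.5% |
| 18 | 0.33 | 15.8% |
| 24 | 0.29 | 9.7% |
| 30 | 0.26 | 6.1% |
| 60 | 0.18 | 0.7% |

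The chance that all three conditions are exactly balanced over the three sessions is about 0.5% at n = 12 and 0.1% at n = 30 (simulation).

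**Effect on the contrast without a session term.** Suppose the within-session response drifts linearly by d residual SDs per session. In units of squared residual SD, the facilitatory-minus-sham contrast then has variance 2/n + d²·(2/n) = (2/n)(1 + d²). At n = 12:

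- d = 0.25: 0.1667 × 1.0625 = 0.177 (simulated 0.177)
- d = 0.5: 0.1667 × 1.25 = 0.208 (simulated 0.200)
- d = 1: 0.1667 × 2 = 0.333 (simulated 0.336)

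**Type I error without a session term.** This was simulated with no treatment effect, for n = 12, 18 and 24, using a paired t-test at an assumed two-sided 5%. Averaged over all orders, the rate stayed between 4.7% and 5.4%. Among only those trials that drew an imbalance of at least half a session, it was about 6% at d = 0.25. At d = 0.5 it was 10% (n = 12) and 14% (n = 24), and at d = 1 it was 14% and 25%.

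**With a session term.** The drift leaves the contrast, and what remains is the price of a non-orthogonal design. Relative to perfect balance, the variance rises on average by about 10% at n = 12, 7% at 18, 5% at 24 and 4% at 30. At n = 12 the term thus saves more than it costs only when d² exceeds about 0.10, that is, when d exceeds about 0.32 SD per session (√0.10 ≈ 0.32). The simulation agrees. At d = 0.25 the variance was 0.184 with the term and 0.177 without it; at d = 1 it was 0.179 and 0.336.

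**With equal use of the six orders.** D averages exactly 0 in each complete block of six. The simulated variance at n = 12 was 0.161 to 0.167 at every drift tried, against 2/12 = 0.167 in theory.

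**Carry-over.** In the six orders, each condition comes first twice and follows each of the other two twice. A condition therefore picks up one third of the carry-over of each other condition, and the unadjusted contrast of A minus B keeps (carry-over of B − carry-over of A)/3. Balance equalises which condition follows which; it does not remove carry-over.

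**The case against.** The strongest case on the other side has four parts.

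First, silence is not simple randomisation. A reader might infer that the sponsor chose unconstrained random orders, but the one sentence also fits allocation to a balanced set of sequences, and the text calls itself an abbreviated protocol. This stands. The figures above apply only if orders are drawn independently, and one sentence disclosing a balanced list would settle the design half of the point.

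Second, random order is already a valid control. This also stands: a reader might infer that the rTMS contrast is biased or that the error rate is inflated, and neither is so on average. The inflated rates arise only after conditioning on an unlucky draw and assuming a sizeable drift.

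Third, the plan has safeguards. Sessions are at least 7 days apart, which limits carry-over. The pre-rTMS reading in each session allows shifts in level from practice or earlier therapy to be removed. That is partly right. The analysis paragraph does not say that the pre-rTMS reading will be used, and using it would not remove a drift in how much subjects respond.

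Fourth, once a session term is fitted, balance gains little. This stands as to size (about 10% of variance at n = 12, 4% at n = 30), but the plan does not name that term.

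**Conclusion.** The point holds as a worthwhile, inexpensive improvement. It does not show that the trial is biased. The plan leaves the spread of conditions over sessions to chance as far as it is described, and names no model term to correct for it. With independent random orders, a facilitatory-minus-sham difference of at least half a session has a chance of about 26% at n = 12, falling to 6% at n = 30 and 0.7% at n = 60. The result is extra noise in the Hypothesis 1a and 1b contrasts, in proportion to any drift across sessions.

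Three assumptions carry this: independent random orders, a small sample, and a drift in within-session response. None is documented. That the trial is small is only an inference from its feasibility and preliminary-efficacy objective, and the documents give no evidence on the size of any drift. A reader might also infer that unbalanced order is what lets carry-over in, and that balanced orders would cure it. The documents do not show that carry-over occurs, and the arithmetic shows that balance alone would not remove it.

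**What to change.** In the Study design overview, replace the allocation sentence with text such as: Subjects will be randomised, in concealed permuted blocks of six, to one of the six possible orders of the facilitatory, inhibitory and sham sessions, so that each condition occurs equally often in each session and follows each other condition equally often. The allocation list will not be available to the assessing therapist. Withholding the list matters because the last order in a block could otherwise be inferred. If a balanced list is already in use, describe it.

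In the Statistical Analysis Plan, state the model: a linear mixed model for the two post-rTMS readings with condition, session, time point, condition-by-time and that session's pre-rTMS value as fixed effects, and subject as a random effect. Add a first-order carry-over term as a sensitivity analysis. State the planned sample size, preferably a multiple of six.

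The cost is a different randomisation list and a few lines of text, with no additional subjects, visits or staff. Two downsides should be acknowledged: an incomplete last block or drop-outs leave a small residual imbalance, and the session term uses two degrees of freedom.

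### Facilitatory and inhibitory rTMS differ by up to 950 s of stimulation between the blinded evaluator's first two tests, and nothing described masks that difference for Hypothesis 1b

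*Combined protocol and SAP*

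**What the plan says.** The Study design overview makes one statement about blinding, and it concerns the assessor: "All evaluations will be performed by a therapist who will be blinded to the site or the type of rTMS". Each patient has three treatment sessions in random order.

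The rTMS intervention section gives the two active protocols: "Facilitatory rTMS protocol will consist of 5Hz rTMS at 90% resting MT; a total of 1250 pulses" and "Inhibitory rTMS protocol will consist of 1Hz rTMS for a total of 1200 pulses". For the control it says "Sham intervention will be provided using a sham coil", with no rate, pulse count or length. It adds that "the sham coil is identical in appearance to the active coil" and that its sound and feel are similar.

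Under Aim 1, the primary outcome is two-point discrimination, measured "by determining subjects' ability to distinguish if the touch consisted of one or two points". Within each session it is taken "once before and 2 times after the rTMS: immediately after and 1 hour after". Hypothesis 1b in the Specific Aims is directional: "Facilitatory rTMS of contralesional S1 produces a greater response versus inhibitory rTMS in improving tactile discrimination".

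The document does not mention equal session lengths, a fixed interval between tests, where the therapist is during stimulation, or any check of the blind.

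**The concern.** The stimulation block sits between the pre-rTMS test and the immediate post-rTMS test, and the blinded therapist performs both. If the block is much longer for one active type, the elapsed time is a cue to the type, even for someone outside the room who never sees or hears the coil. The sham coil protects active against sham. It has no bearing on 5 Hz against 1 Hz, which is the contrast in Hypothesis 1b.

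The outcome is the patient's one-or-two answer to disks that the examiner applies and scores. An examiner who has inferred the type, and who expects facilitatory stimulation to do better, could influence how the test is given or scored. The Statistical Analysis Plan offers linear mixed models. These cannot separate an assessor effect that follows rTMS type from an effect of rTMS, and enrolling more patients would not help. Protection has to come from how the sessions are run.

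Hypothesis 1a is exposed to the same timing cue only if the sham session does not match the 5 Hz session in length. The document leaves that open.

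**Working it through.** The plan states no stimulation times, so there is no figure to reproduce. They follow from the stated rates and pulse counts.

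**Inputs** (rTMS intervention section): facilitatory, 1250 pulses at 5 Hz; inhibitory, 1200 pulses at 1 Hz. Not given: the train structure and pauses of the 5 Hz protocol, and the rate and length of sham.

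**Pulse-delivery time** = pulses / rate.
- Facilitatory: 1250 / 5 = 250 s (4.2 min).
- Inhibitory: 1200 / 1 = 1200 s (20 min).
- Difference: 1200 − 250 = 950 s (15.8 min). Ratio: 1200 / 250 = 4.8.

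**Effect of pauses (assumed).** With total rest R in the 5 Hz session, the difference is 950 − R seconds.

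| Total rest R | 5 Hz session | Difference from 1 Hz session |
|---|---|---|
| 0 s | 250 s | 950 s (15.8 min) |
| 60 s | 310 s | 890 s (14.8 min) |
| 240 s | 490 s | 710 s (11.8 min) |
| 600 s | 850 s | 350 s (5.8 min) |
| 950 s | 1200 s | 0 |

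R depends on both the number of trains and the pause length, and neither is stated. With 25 trains (24 pauses) of 20 s, R = 480 s and the difference is 470 s (7.8 min). With 50 trains (49 pauses) of 20 s, R = 980 s, so the 5 Hz session lasts 1230 s and is 30 s longer than the 1 Hz session. So 950 s is the upper end of the range, and the cue can vanish.

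**Effect of other session content.** Anything of equal length in both sessions leaves the difference unchanged. If 300 s of peripheral stimulation fell before the post-test, the times would be 550 s and 1500 s, still 950 s apart. Content of variable length would blur the cue without removing the average difference.

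**Sham.** If sham is run like the 5 Hz session, timing does not separate sham from facilitatory, and the inhibitory session is the one that stands out. If sham is run like the 1 Hz session, the facilitatory session stands out and Hypothesis 1a is exposed too.

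**The case against.** The strongest reply is that the blind is promised and only its mechanics are missing, from a text that calls itself an abbreviated protocol. Where the therapist waits and how the post-test is called are details such a text may omit. For bias to arise, the evaluator must also know the protocol lengths, be able to observe the interval, infer the type, favour Hypothesis 1b, and let that shift an answer the patient gives. The document establishes none of these links. Coil targeting, SEP recording (500 epochs at 3 Hz, 500 / 3 ≈ 167 s or 2.8 min per block) and peripheral stimulation may also fall within the interval and make it less informative. All of this stands, and it limits the point to a risk.

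It does not remove the point. Unless long pauses happen to equalise the sessions, running them as written builds the cue in, and nothing described takes it out.

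A reader might go further and infer that the blind fails, or that an evaluator would usually guess right. The document does not support either. A guess rate needs an assumed pause pattern and an assumed SD for other session time. With no pauses and a cut at the midpoint, Φ(15.83 / (2 × SD)) gives 94% at an SD of 5 min, 79% at 10 min and 65% at 20 min. With 50 trains and 20 s pauses it is close to the 50% expected by chance. These figures are illustrative only, and no conclusion here rests on them.

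It is also fair to say that the patient, who gives the response, can perceive 5 Hz against 1 Hz directly. No change to the evaluator's procedure cures that.

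**Conclusion.** The point holds as an avoidable route to assessor unblinding for Hypothesis 1b. The stated protocols differ by up to 950 s (15.8 min) between the evaluator's pre-test and immediate post-test, and the one masking feature described does not address it. The 950 s assumes no pauses. It shrinks second for second with rest in the 5 Hz session and is zero at 950 s of rest. The cue matters only if the evaluator can observe the interval and knows what it means, which the document neither says nor rules out. Whether unblinding occurs and how large any bias would be are both unknown.

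For a study of feasibility and preliminary efficacy this is a cheap improvement worth making, not a fatal flaw. Even when it is made, Hypothesis 1b remains incompletely blinded on the patient's side.

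**What to change.** Add to the rTMS intervention section, in words such as these:

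> All three sessions use the same fixed stimulation slot, starting when set-up is complete. The slot lasts 20 minutes, or as long as the longest protocol including pauses. Shorter stimulation starts later, so that every type ends when the slot ends, and the immediate post-rTMS evaluation follows. The evaluator remains out of sight and hearing during the slot and is not told when pulses begin. Sham is delivered with the timing of the 5 Hz, 1250-pulse protocol, including its pauses.

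Also state the train and pause structure of the 5 Hz protocol, and list as a limitation of Hypothesis 1b that patients can perceive the difference in rate. Having the evaluator and patient record a guess of rTMS type after the last evaluation of each session is optional. It costs one line on the session form.

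With a 20-minute slot, the cost is at most 950 s (about 16 min) of waiting in each 5 Hz or sham session, or 2 × 950 = 1900 s (about 32 min) per patient over three sessions, and less if there are pauses. Dose, the immediate post-test and the 1-hour test are unchanged.
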